### **Collection of blood samples**

Blood samples will be collected in fasting condition, from an antecubital vein in tubes containing or not EDTA anticoagulants. After blood clotting or not, the tube will be centrifuged at 2500 rpm for 10min to obtain 500 µl of serum or plasma, which will be stored at -80°C for later use to determine circulating cells and serum/plasmatic parameters, as described below.

### **Blood cell count**

Blood cell count will be carried out on the same day using blood obtained in a tube containing EDTA. All subjects must be hydrated at the time of collection. Cell counts (erythrocytes, leukocytes, and platelets) will be performed using the automated system Coulter brand AcTDiff model (Beckman Coulter, USA).

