In terms of the effects of lactobacilli supplementation in a physical exercise context, although they are still scarce, a longitudinal study carried out with the supplementation of *Lactobacillus rhamnosus* for 3 months found a decrease in duration and severity, but not in the incidence of URTI in athletes (Kekkonen, 2007). Beyond this report, Gleeson et al. (2011), observed a reduction in the frequency of URTI in association with an increase in salivary levels of immunoglobulin A (IgA), in athletes supplemented with LcS for about 4 months. Moreover, our group was able to demonstrate that marathon runners supplemented with fermented milk containing 40 billion of LcS for a period of 30 days before the marathon, not only presented a lower incidence and duration of upper respiratory symptoms (URS) but also highlighted the ability of this bacteria in modulating the immune/inflammatory responses, both systemic and in the upper airway, specifically after the marathon performance ([name], 2019).

Like the marathon race, the triathlon is recognized as a high-intensity sport, in which the athletes are submitted to a strenuous and prolonged competition with remarkable physiological impacts (O'Toole M.L., 1989). In this sense, triathletes are particularly prone to muscle injuries and fatigue (Kienstra C.M., 2017), not only as a result of mechanical but also inflammatory stress, which can induce muscle damage associated with this sport modality (Howatson G., 2008). Furthermore, triathlon competition also stimulates the production of reactive oxygen species (ROS) due to excessive aerobic respiration, ischemia-reperfusion, and leukocyte activation (He F., 2016) in response to the pattern of long duration and exposure to environmental conditions that favor dehydration, as well as the depletion of carbohydrates can

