### **Sample collection**

Blood, saliva, and nasal swab will be collected on five different occasions: (1) before the beginning of the ingestion of fermented milk containing LcS or placebo; (2) 24 hours before the triathlon competition; (3) immediately (IM); (4) 72 hours (post-72h); and (5) 14 days after the competition, as shown in Figure 1. In addition, on the same occasions, the occurrence of upper airway symptoms and mood states will also be assessed by using questionnaires.

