### **Determination of cytokine concentration**

The concentration of cytokines IL-1β, IL-1ra, IL-4, IL-5, IL-6, IL-10, IL-12p70, IL13, IL-17A, and TNF-alpha, both in serum, saliva, as in the whole blood culture supernatant, stimulated or not with LPS (Lipopolysaccharide), will be determined by using LEGENPlex for human cytokines, which is based on a bead system (BioLegend, San Diego, CA, USA), following manufacturer's instructions. The cytokine concentrations will be calculated from the

values of their respective standard curves, obtained at the same time as the evaluation of the samples.

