### **Statistical analysis**

All data obtained during the development of this study will be added to a unique file, preferentially in an Excel file, which will be available to all researchers not only to consult and check the data quality/accuracy but also to add any results through GOOGLE-DRIVE. It is noteworthy to clarify that, to perform all the statistical analysis proposed here, we will follow the "intention-to-treat" (ITT) analysis, not only because it is recommended as an analysis strategy for randomized studies but also to be possible to maintain the sample size, as well as to use the data obtained from the participants regardless of whether they complete the study since ITT considers all randomized participants in the analysis, whether they drop out or not. In addition, the multiple imputation (MI) method will be applied to handle missing data since

MI fills in missing values by generating plausible numbers derived from distributions of and relationships among observed variables in the data set. Beyond these analyses, in order to check and increase the reliability of the results obtained in the ITT analysis, we also intend to conduct the statistical analysis regarding the per-protocol (PP) analysis, which will be used exclusively the complete data obtained from the volunteers.

After all data will be added to the Excel file and the data quality/accuracy is checked by the researchers, these data will be initially compared with the Gaussian curve, and normality determined for each variable.

If the variable presents a parametric behavior, the mean and standard deviation will be used, and they will be compared by using the ANOVA test for repeated measures with post hoc tests for intragroup (longitudinal) and intergroup (cross-sectional) analysis.

On the other hand, if the data present a non-parametric behavior, they will be represented by median and interquartile ranges, and they will be compared by using Friedman's test with Müller-Dun post hoc test for intragroup (longitudinal) and the Kruskal-Wallis test with Müller Dunn's post hoc test for intergroup (cross-sectional).

Using Pearson (for parametric values) or Spearman tests (for non-parametric values), the correlation between the variables studied will be evaluated.

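### Per-volume blood measures are compared within each arm between rest and the immediate post-race draw with no correction for plasma-volume change, so haemoconcentration alone can look like a race response

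*Combined protocol and SAP*

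**What the plan says.** The Sample collection section sets five occasions. The first two precede the race. The others are "3) immediately (IM); (4) 72 hours (post-72h); and (5) 14 days after the competition". The Triathlon competition section describes 1,900 m of swimming, 90 km of cycling and 21 km of running.

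The blood measures at issue are all amounts per volume:

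- Blood cell count: "Cell counts (erythrocytes, leukocytes, and platelets) will be performed using the automated system Coulter brand AcTDiff model". Haematocrit and haemoglobin are not listed.
- Determination of cytokine concentration: serum values are read off a standard curve, with no further adjustment.
- Determination of the systemic concentration of BDNF and hormones: BDNF, cortisol, hGH and sex hormones are serum concentrations.

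The conditions at the draw are stated once for all occasions. The Collection of blood samples section says "Blood samples will be collected in fasting condition". The Blood cell count section says "All subjects must be hydrated at the time of collection". Neither makes separate provision for the immediate post-race draw. The hydration sentence has no definition, measurement, threshold or action if it is not met. The Introduction describes triathlon as involving "long duration and exposure to environmental conditions that favor dehydration".

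For normally distributed variables the Statistical analysis section plans an "ANOVA test for repeated measures with post hoc tests for intragroup (longitudinal) and intergroup (cross-sectional) analysis". Otherwise it plans Friedman's test within groups and Kruskal-Wallis between groups. It mentions no plasma-volume correction or covariate, and neither does any other section available for review.

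**The concern.** When plasma water is lost, everything dissolved or suspended in the remaining blood becomes more concentrated, although nothing has been released. A rest versus post-race comparison of uncorrected concentrations therefore mixes two things: a true change in the amount of an analyte, and a change in the volume it is dissolved in. The planned intragroup tests cannot separate them. The secondary objective concerns systemic responses before and after the competition, so this comparison will be reported.

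The risk grows if within-arm tests are read side by side. The non-parametric route has no group-by-time test. Suppose the artefact is flagged with probability 0.55 in each arm and LcS has no effect. With independent arms, one arm is then significant and the other not in 2 × 0.55 × 0.45 = 49.5% of trials. Without the artefact the figure is 2 × 0.05 × 0.95 = 9.5%. That pattern invites a conclusion about LcS that no between-arm test supports.

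**Working it through.** **The plan's own figure.** The sample size is for salivary IgA: f = 0.15, alpha 0.05, power 0.85, two groups, five measurements, correlation 0.5, epsilon 1. With lambda = f² × N × m / (1 − rho), N = 62 gives 0.0225 × 62 × 5 / 0.5 = 13.95 on 4 and 240 degrees of freedom, and power 0.857. N = 60 gives 0.844. The stated 62 reproduces as the smallest even number. This point neither depends on it nor changes it.

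**Inputs for the artefact.**

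- From the documents: 35–40 athletes per arm (37 used) and alpha 0.05.
- From the documents but borrowed: correlation 0.5, which the plan gives for salivary IgA and which is assumed here to apply to blood.
- Assumed, because the documents give no value: plasma loss L of 5, 10 or 15%; resting haematocrit 0.45; SD of log concentration 0.3, with 0.2 and 0.5 as a range.

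**Size of the rise with no true change.**

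- Serum analyte: 1/(1 − L) − 1.
- Whole-blood count: 1/[(1 − Hct)(1 − L) + Hct] − 1. Red cells keep their volume, so blood shrinks less than plasma. For L = 10% this is 1/(0.55 × 0.90 + 0.45) − 1 = 1/0.945 − 1 = 5.8%.

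**Chance of declaring a change within one arm.** Two-sided paired t-test with 36 degrees of freedom. SD of the difference = SD × √(2(1 − 0.5)) = SD. Non-centrality = log shift × √37 / SD. For serum at SD 0.3, the log shifts 0.0513, 0.1054 and 0.1625 give 1.04, 2.14 and 3.30, against a critical value of 2.03. For counts, the log shifts 0.0279, 0.0566 and 0.0861 give 0.57, 1.15 and 1.75.

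| | 5% loss | 10% loss | 15% loss |
|---|---|---|---|
| Rise, serum analyte | 5.3% | 11.1% | 17.6% |
| Rise, whole-blood count | 2.8% | 5.8% | 9.0% |
| Flagged, serum, SD 0.3, unadjusted | 17% | 55% | 89% |
| Flagged, count, SD 0.3, unadjusted | 9% | 20% | 40% |
| Flagged, serum, SD 0.3, Bonferroni over 10 | 3% | 22% | 62% |
| Flagged, serum, SD 0.2, unadjusted | 33% | 88% | nearly 100% |
| Flagged, serum, SD 0.5, unadjusted | 9% | 24% | 49% |

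The Bonferroni row uses alpha = 0.05/10 = 0.005, because five occasions give ten pairs. Its reference rate is 0.5% per comparison; for the other rows it is 5%.

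**Between arms.** Equal loss in both arms multiplies both means by the same factor, so the ratio is 1.00 and no bias arises. Unequal loss would matter: 10% in one arm and 5% in the other gives 0.95/0.90 = 1.056. Randomisation gives no reason to expect such a difference, but the plan records nothing that would reveal one.

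**The case against.** The strongest reply is that the trial asks about LcS, in a randomised blinded comparison, and a volume effect common to both arms cancels there. That stands. A reader might infer that haemoconcentration biases the LcS versus placebo contrast or threatens the primary endpoint. The documents support neither: allocation is 1:1 and random, and IgA is measured in saliva. Extra noise between arms is also slight. If log plasma volume varies between athletes with SD 0.05 (assumed), an SD of 0.3 becomes √(0.09 + 0.0025) = 0.304, an increase of 1.4%.

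The rejection rates depend heavily on assumptions. That stands too. At an assumed log SD of 0.8, a 10% loss is flagged in only 12% of trials. The plan does not name the parametric post hoc adjustment, and a strict one cuts the rates considerably. Serum rates must not be applied to cell counts, where the rise is about half as large.

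A reader might also infer that hydration at the post-race draw is impossible. The Introduction says conditions favour dehydration. It does not say that every finisher is dehydrated or cannot drink during the race. The hydration sentence is a control in intent. However, it is unmeasured, and being hydrated at the draw would not show that plasma volume had returned to its resting value.

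Finally, it is tempting to say that the correction needs only values already collected. The listed erythrocyte count gives blood-volume change, but plasma-volume change also needs haematocrit, which the section does not list.

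**Conclusion.** The point holds, within limits. Followed as written, the plan can report lost plasma water as a systemic race response in the intragroup comparisons of cell counts, serum cytokines, BDNF and hormones. Over assumed losses of 5–15%, the artefact is a rise of 5.3–17.6% in serum and 2.8–9.0% in counts. At log SD 0.3, unadjusted tests flag it in 17–89% and 9–40% of trials respectively. These figures rest on assumed plasma loss, haematocrit and SD, and on a correlation borrowed from salivary IgA. Analytes with low variability or small true changes are most exposed; a large true response would dwarf the artefact.

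The consequence is confined to secondary within-arm time effects. The sample size, the primary endpoint and the expected arm contrast are untouched. This is a change worth making before the race, because an index not recorded at the draw may not be recoverable later.

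**What to change.** 1. Reconcile the hydration condition in the Blood cell count section with the immediate post-race draw in the Sample collection section. How athletes' hydration is managed is for the investigators; the two sections need to agree, and the text should say what is recorded.
2. State in the Blood cell count section that haematocrit, and haemoglobin if available, is recorded with the erythrocyte count at every draw.
3. In the Statistical analysis section, report intragroup comparisons involving the post-race draw both uncorrected and corrected, and name the resting draw used as reference. Blood-volume ratio (post/rest) = erythrocytes at rest / erythrocytes post. Plasma-volume ratio = blood-volume ratio × (1 − Hct post)/(1 − Hct rest). Multiply leukocyte and platelet counts by the first ratio and serum concentrations by the second. The erythrocyte count is the yardstick here and becomes constant by construction, so report it uncorrected only.
4. State that conclusions about LcS rest on the between-arm contrast, not on comparing within-arm significance.

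The cost is a second column of results, a little added measurement error from the count, and the recording of an index that the section does not now list. The number of participants and the visits do not change.

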### **Whole blood culture**

A volume of 100µL of the blood sample will be mixed with 900µL of culture medium, containing 10% fetal bovine serum + RPMI 1640, and will be incubated for 48 hours in 48 well plates, maintained in an air-conditioned oven with 95% oxygen and 5% carbon dioxide at

37°C. At the same time point, another well containing the same mixture of blood and medium will be submitted to stimulation with lipopolysaccharide (LPS) and maintained under the same conditions as previously reported. After the incubation period, the culture supernatant will be collected and centrifuged at 1400 rpm for 10 minutes, and a volume of, at least, 500µL will be frozen at 80°C for further evaluation of cytokine concentration.

### **Saliva sample collection**

Two milliliters (2 mL) of saliva samples will be collected from each volunteer directly in 15 mL sterile Falcon tubes, without stimulation. After collection, each sample will be maintained at 4°C until to be centrifuged at 3000 rpm for 10 minutes at 4°C. After that, 500µL of the supernatant will be transferred to 1.5 mL conical tubes and frozen at -80°C for further later determination of the concentration of cytokines, IgAs, and antibacterial peptides, without adding a preservation medium.

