## ABSTRACT

Triathlon, as a sport that combines high-intensity and long duration, imposes the body to an expressive physiological adaptation. However, when the challenge exceeds the physiological adaptation capacity, it is possible to observe the occurrence of several disorders in the athlete's health. In this sense, among several factors that can help in this adaptation, it has been pointed out that the microbiota, which can be modulated by diet, age, medical treatments, lifestyle, and physical exercise, can favor the maintenance of a healthy status. According to the literature, both probiotics, prebiotics, and symbiotics are able to benefit people in different ways, for instance, by favoring immunoregulation, these elements can impact the prevention or decrease in the frequency and/or intensity of infections in the upper airways, both in the population in general and in athletes. However, it is noteworthy to mention that there is still a lack of reports in the scientific literature on the effects of the ingestion of fermented milk containing *Lacticaseibacillus paracasei* strain Shirota (LcS), a well-known probiotic agent, not only on the modulation of the immune/inflammatory responses, but on the manifestation of symptoms of airways and mood state in triathletes. Therefore, in this study, we aimed to investigate, in a general way, the effect of daily intake of fermented milk containing 40 billion LcS in amateur triathletes, emphasizing that our primary endpoint will be to evaluate the concentration of salivary IgA, and the secondary endpoints will be to assess both systemic immune/inflammatory and upper airway responses, as well as the incidence and duration of upper airway symptoms, and also the mood states. In order to respond to these endpoints, samples of saliva, nasal swab, and blood, as well as data regarding quality of life, upper airway symptoms manifestation, and mood states will be obtained on five different occasions: 30 days (1) and 24 hours before the competition (2), and also immediately (3), 72 hours (4), and 14 days after the competition end (5). It is important to highlight that the data related to the quality of life, upper airway symptoms manifestation, and mood states will be obtained by using specific and validated questionnaires, such as SF-36 (Short Form Health Survey 36), WURSS-21 (Wisconsin Upper Respiratory Symptom Survey – 21), and BRUMS (The Brunel Mood Scale), respectively. Finally, it is also paramount to clarify that the triathletes participating in this study will be oriented to ingest a daily bottle of fermented milk containing 40 billion LcS or placebo/unfermented milk throughout the study period, starting the ingestion

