## **OBJECTIVES**

### **PRIMARY**

Investigate the effect of daily ingestion of fermented milk containing 40 billion LcS on the changes in the concentration of salivary IgA in amateur triathletes participating in this study, before and after an official triathlon competition.

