### **Determination of the concentration of IgAs and antimicrobial peptides**

The salivary concentration of IgAs and the antibacterial peptides [LL-37 (cathelicidin), defensin-1, lactoferrin, and lysozyme] will be determined using ELISA commercial kits (Biosay Technology Laboratory, Shanghai, China), in accordance with the manufacturer's instructions.

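### Saliva collection is untimed, so a post-race change in IgA concentration cannot be separated from a change in saliva flow in the planned within-group before/after tests

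*Combined protocol and SAP*

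**What the plan says.** The Abstract states that "our primary endpoint will be to evaluate the concentration of salivary IgA". The primary objective is the effect of the fermented milk on "changes in the concentration of salivary IgA in amateur triathletes participating in this study, before and after an official triathlon competition".

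Under Saliva sample collection, "Two milliliters (2 mL) of saliva samples will be collected" and these "saliva samples will be collected from each volunteer directly in 15 mL sterile Falcon tubes, without stimulation". No duration, start or stop time, or flow rate is recorded. The assay section reports "The salivary concentration of IgAs and the antibacterial peptides" by ELISA. No section mentions a secretion rate or any adjustment for total protein or osmolality.

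Sample collection sets two occasions before the race and then "3) immediately (IM); (4) 72 hours (post-72h); and (5) 14 days after the competition". So one of the five samples is taken directly after the event. The Introduction describes triathlon as involving "long duration and exposure to environmental conditions that favor dehydration".

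The Blood cell count section asks that participants be hydrated when sampled. It gives no method or check and does not mention saliva.

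Statistical analysis plans both within-group (longitudinal) and between-group tests, whether the parametric or the non-parametric route is taken.

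**The concern.** Concentration is the ratio of IgA output to saliva flow. Anything that lowers flow raises concentration, even if the glands secrete the same amount of IgA per minute. The reverse also holds: a real fall in output can be hidden by an equal proportional fall in flow.

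The sample most exposed to this is the one taken straight after the race, which is also where a before/after comparison is of most interest. A within-group rise from baseline to that sample could reflect mucosal immunity, a drier mouth, or both. With a fixed volume and no clock, the plan discards the one measurement that would distinguish them. Collection time cannot be recovered later from a frozen aliquot.

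What is at stake is how the within-group IgA course is interpreted. The validity of the randomised comparison is not in question.

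**Working it through.** **1. The plan's own sample size.** Inputs from Population and design of the study: f = 0.15, α = 0.05, power 0.85, correlation 0.5, nonsphericity correction 1, two groups, five measurements. For the within-between interaction:

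- λ = f² × N × m / (1 − ρ) = 0.0225 × 62 × 5 / 0.5 = 13.95
- df1 = 4; df2 = 4 × (62 − 2) = 240
- Power from the noncentral F is 0.857 at N = 62 and 0.844 at N = 60.

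The smallest even N that reaches 0.85 is 62, so the stated figure reproduces. The calculation targets the group-by-time interaction, a between-arm question. It has no explicit term for saliva flow.

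**2. Effect of flow on concentration.** With output S and flow V, concentration C = S / V. If S is constant and V falls by a proportion x, the relative rise in C is 1/(1 − x) − 1.

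| Assumed fall in flow | Rise in concentration |
|---|---|
| 25% | 1/0.75 − 1 = 33% |
| 40% | 1/0.60 − 1 = 67% |
| 50% | 1/0.50 − 1 = 100% |

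Both the flow falls and the constant output are assumptions.

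**3. Why timing resolves it.** For a 2 mL sample collected in T minutes, flow is 2/T and secretion rate is C × 2/T. If flow falls by 40% and output is constant, C and T are each multiplied by 1/0.60 = 1.67. Their ratio, and so the secretion rate, is unchanged. The missing collection time carries exactly the information needed.

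**4. Within-group test, illustration.** Assumptions: 31 per arm (62/2), log-SD of IgA 0.5, correlation 0.5, person-to-person log-SD of the flow change 0.2, no true change in output, and an unadjusted two-sided paired test at 0.05.

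- Variance of the log difference = 2 × 0.5² × (1 − 0.5) + 0.2² = 0.29, so SD = 0.539
- SE = 0.539 / √31 = 0.097
- Flow fall of 10%: −ln(0.9) = 0.105, or 1.1 SE; significant in about 18% of trials
- Flow fall of 20%: −ln(0.8) = 0.223, or 2.3 SE; about 60%
- Flow fall of 30%: −ln(0.7) = 0.357, or 3.7 SE; about 94%

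The percentages come from 3,000 simulated trials per scenario. A multiplicity-adjusted post hoc test would give lower figures.

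**5. Between-arm test under the same assumptions.** When flow falls equally in both arms by 0% to 50%, the group-by-time test rejects in 4.2% to 5.9% of null trials on the log scale. On the raw scale it reaches 8.1%, at a 50% fall. The arm contrast is essentially protected.

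**The case against.** The strongest reply is that the primary objective concerns the effect of the product on the IgA change, and the trial is sized on the group-by-time interaction. Both arms race, allocation is random and blinded, and a shared fall in flow does not bias that contrast on average. This stands, and it confines the point to the within-group tests.

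A reader might infer that the primary comparison itself is biased. That needs flow to differ by arm. If a mean 30% fall were smaller in one arm by 5, 10 or 15 percentage points, the interaction test would reject in about 8%, 16% or 28% of null simulated trials. Nothing in the documents suggests such a difference.

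A reader might also infer that flow variation leaves the trial underpowered. Adding a log-SD of 0.2 to 0.5 for flow change to the simulation at N = 62 cuts power from about 88% to between 82% and 65%. But the plan says its parameters came from salivary IgA data in an earlier marathon study. If that saliva was untimed too, f = 0.15 already contains flow variation and adding it again counts it twice. The documents do not settle this. Enrolment is also set at 70 to 80, where the plan's own inputs give power of 0.90 to 0.94 before dropout.

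Three further replies have some force:

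- Concentration is a legitimate endpoint, and only one of the five samples is taken directly after the race.
- The Introduction links dehydration to fatigue and gastrointestinal problems, among others, but does not mention saliva flow.
- A reference such as total protein could be assayed from the frozen supernatant if volume allows. None is planned, however, and this would not recover flow.

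The hydration line under Blood cell count is at most partial mitigation, because it does not measure flow.

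**Conclusion.** The point holds as a limit on interpretation. As written, the plan cannot tell a change in IgA output from a change in saliva flow in its within-group before/after tests. The exposure is clearest at the sample taken straight after the race.

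The size is unknown, because the documents contain no flow data. Under constant output, assumed flow falls of 25% to 50% correspond to rises in concentration of 33% to 100%. The documents support neither bias in the randomised contrast nor a loss of power, and neither is claimed here.

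This takes the protocol's own primary endpoint as given; the ethics opinion in the same file names upper airway symptoms instead. The change is a cheap improvement worth making before the first sample, because unrecorded collection times cannot be reconstructed.

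**What to change.** - **Saliva sample collection:** record the start time, stop time and actual volume of every saliva collection at all five occasions.
- **Statistical analysis:** define flow (mL/min) and IgA secretion rate (concentration × flow). Pre-specify secretion rate as a supportive analysis of the primary endpoint, using the same model and occasions. Keep concentration as primary, so the sample size is unchanged.
- **Reporting:** state that a within-group change in concentration straight after the race will be interpreted alongside flow and secretion rate.

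The cost is a stopwatch, one data column for timing (plus the measured volume) and one extra analysis. The downside is that secretion rate has its own variability, which is a reason to keep it supportive. The same timing would also help in reading the salivary cytokines and antimicrobial peptides, which are likewise reported as concentrations.
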